The differences in blind-side detection improvement rates between MPPs and FPPs will be analyzed using a McNemar test for data combined across both periods of the crossover, testing the hypotheses that improvements rates will be higher with MPPs than with FPPs at the 40° bearing angle (primary hypothesis) but will not differ at 20° (secondary hypothesis). An intention to treat analysis will be used. Participants who withdraw after treatment allocation but before the end of the crossover will be categorized as no improvement for both types of prism glasses. Questionnaire responses will be analyzed with non-parametric statistics. An α -value ≤ 0.01 will be considered to indicate statistical significance for the primary analysis and ≤ 0.05 for the secondary analyses

Sample size estimate:

The sample size calculation is based on results from a small pilot study ($n = 6$) conducted in [name] lab at Schepens in which participants with hemianopia completed measurements of collision detection using the same test as in the clinical trial. The sample size is computed for the primary outcome based on a McNemar test for a 2-by-2 contingency table of the binary improvement (yes/no) for MPPs and FPPs for detection of 40° pedestrians with data combined across both periods of the crossover. In the lab-based pilot study, 100% of participants improved with MPPs for the 40° pedestrians and 33% improved with FPPs. For the clinical trial, we anticipate that some participants will not show improvement with MPPs, and the overall effect size will be smaller. We therefore estimate that 70% of participants will improve with MPPs and 25% will improve with FPPs. The minimum sample size to detect a 45% difference between the proportion of participants improving with MPPs and FPPs is 36 participants, assuming 20% overlap (i.e. improved with both MPPs and FPPs), power of 90% and significance (alpha) level of 1%, 2-tailed test. Allowing for 30% failing to meet inclusion criteria and 20% attrition after starting the clinical trial, we estimate a total sample size of 54 participants.

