Based on prior multi-site clinical trials of prism glasses for HH ([name] et al., 2014), we expect that up to 30% of enrolled participants may fail to meet the inclusion criteria and 20% may withdraw after treatment allocation. Therefore, we will need to enroll at least 55 participants in total (as screening is done at the first visit). In addition, prior to the main clinical trial, we plan to conduct a pilot of the clinical trial at Schepens and Mass Eye and Ear to verify study procedures and generate data to verify the sample size calculation. We plan to enroll 10 participants for the pilot clinical trial. Therefore, the total enrollment will be 65 participants.

10. Monitoring and Quality Assurance

Adverse event criteria and reporting procedures

Criteria to define adverse events:

This protocol uses the definition of adverse event from 21 CFR 312.32 (a): any untoward medical occurrence associated with the use of an intervention in humans, ***whether or not considered intervention-related***.

- **Serious adverse event** means any event temporally associated with the subject's participation in research that meets any of the following criteria:
 - results in death;
 - is life threatening (places the subject at immediate risk of death from the event as it occurred);
 - requires inpatient hospitalization;
 - results in a persistent or significant disability/incapacity; or
 - any other adverse event that, based upon appropriate medical judgment, may jeopardize the subject's health and may require medical intervention to prevent one of the outcomes listed above.

Unanticipated Problems:

Any incident, experience, or outcome that meets all of the following criteria:

- It is unexpected (in terms of nature, severity (see severity grades below), or frequency) given (a) the research procedures that are described in the protocol-related documents, such as protocol and informed consent documents; and (b) the characteristics of the subject population being studied;
- It is related or possibly related to participation in the research (possibly related means there is a reasonable possibility that the incident, experience, or outcome may have been caused by the procedures involved in the research); and
- It suggests that the research places subjects or others at a greater risk of harm (including physical, psychological, economic, or social harm) than was previously known or recognized.

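### The enrolment target adds the two loss rates to 36 instead of dividing by the retention rates, so 55 enrolled give about 31 completers and power below the stated 90%.

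*Combined protocol and SAP*

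**What the plan says.** All the figures are in Section 9, under the sample size estimate. The calculation is "based on a McNemar test for a 2-by-2 contingency table of the binary improvement (yes/no) for MPPs and FPPs" at the 40° bearing angle. Its inputs are "We therefore estimate that 70% of participants will improve with MPPs and 25% will improve with FPPs", "assuming 20% overlap (i.e. improved with both MPPs and FPPs", and "power of 90% and significance (alpha) level of 1%, 2-tailed test". The result is "The minimum sample size to detect a 45% difference between the proportion of participants improving with MPPs and FPPs is 36 participants". The first paragraph then inflates for losses: "30% failing to meet inclusion criteria and 20% attrition after starting the clinical trial, we estimate a total sample size of 54 participants".

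The second paragraph states what each loss rate applies to: "up to 30% of enrolled participants may fail to meet the inclusion criteria and 20% may withdraw after treatment allocation". It continues: "Therefore, we will need to enroll at least 55 participants in total", and notes that screening takes place at the first visit, so this is a count before screening. It then adds a separate pilot of 10, run before the main trial to test procedures and check the sample size assumptions, for a total of 65.

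The data analysis plan in the same section scores anyone who withdraws between allocation and the end of the crossover as not improved on either device.

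**The concern.** Participants first pass or fail screening, and some of those allocated then withdraw. To finish with 36, one divides by the proportion retained at each step. Adding the two percentages to 1 and multiplying always gives too small a number. The stated 54 looks like that additive calculation, and 55 is 54 plus one.

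At stake is the stated power of the primary comparison. If the main phase enrols 55 and losses run as planned, it has fewer completers than the plan's own minimum, and the 90% figure does not describe the trial. The two paragraphs also give different totals (54, and at least 55). That gap is trivial, but one number should be used.

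**Working it through.** **Inputs, all from Section 9.** Improvement rates 0.70 (MPP) and 0.25 (FPP); improved with both 0.20; two-sided alpha 0.01; power 0.90; screen failure 0.30 of those enrolled; withdrawal 0.20 of those allocated.

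**1. Reproduce 36.** The discordant cells are p10 = 0.70 − 0.20 = 0.50 and p01 = 0.25 − 0.20 = 0.05. Their sum is 0.55 and their difference d is 0.45. The unconditional McNemar formula gives

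n = [2.576·√0.55 + 1.2816·√(0.55 − 0.45²)]² / 0.45² = 35.1, so 36.

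Exact McNemar, summing over the possible numbers of discordant pairs, also needs 36 (power 90.6%). The base figure is sound.

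**2. Find where 54 comes from.**

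| Inflation of 36 | Result |
|---|---|
| 36 × (1 + 0.30 + 0.20) | 54.0 |
| 36 × 1.3 × 1.2 | 56.2 |
| 36/0.80 | 45.0 |
| 36/0.70 | 51.4 |
| 36/(0.70 × 0.80) | 64.3 |
| 36/(1 − 0.50) | 72.0 |

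Only the additive version gives 54. The plan does not print the product, so this origin is inferred. However 54 was obtained, it does not meet the stated loss rates.

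**3. Correct inflation.** Allocated: 36/0.80 = 45. Enrolled: 45/0.70 = 64.3, so 65.

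**4. Completers from the planned enrolment.** The retained proportion is 0.70 × 0.80 = 0.56.

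- 54 × 0.56 = 30.2
- 55 × 0.56 = 30.8
- 65 × 0.56 = 36.4

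The shortfall at 55 is 36 − 30.8 = 5.2, or 5.2/36 = 14%.

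**5. Power at those numbers.** From the formula in step 1, power = Φ{[0.45·√n − 2.576·√0.55]/√0.3475}.

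| Completers | Same formula | Exact McNemar | Uncorrected chi-square |
|---|---|---|---|
| 30 | 82.7% | 81.2% | 86.7% |
| 31 | 84.4% | 83.2% | 88.2% |
| 36 | 91.0% | 90.6% | 93.6% |

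The uncorrected chi-square reaches 90% with 33, so it is not the basis of the stated 36.

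**6. Does the intention-to-treat rule recover the loss?** Scoring withdrawals as not improved on both devices makes them concordant pairs, which McNemar ignores. With 20% of those allocated scored this way, the cells become p10 = 0.40 and p01 = 0.04. Since 55 × 0.70 = 38.5, take 38 or 39 allocated: power is 82.0% or 83.4% by the formula and 81.4% or 83.0% exact. With 45 allocated it is 89.8% and 90.1%. The rule changes nothing material.

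**The case against.** **The 30% is worded as an upper limit and the 55 as a minimum.** True of the second paragraph. With 20% attrition, 55 enrolled give 33.0 completers at 25% screen failure, 35.2 at 20% and 36.1 at 18%, so 55 is enough only if screen failure is about 18% or less (36/0.80 = 45; 1 − 45/55 = 0.18). But the first paragraph sizes the trial for a flat 30%, and that is the assumption behind the quoted power.

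**Total enrolment is 65, the corrected figure.** Section 4 describes the pilot as one of two phases of the clinical trial, and no section expressly excludes pilot participants from the analysis. If they were pooled, 65 × 0.56 = 36.4 and the gap would close. Section 9, however, derives 55 for the main trial first, adds the 10 separately with a different purpose, and never places them in the primary analysis. The match with 65 is not stated as intended.

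**The 70% and 25% might already count withdrawals as failures.** Then only screen failure would need inflation (36/0.70 = 51.4, so 52), and 38 allocated would give about 93% power. This does not fit the text, which adds attrition on top of 36.

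**The effect is modest.** This stands in part. The error does not bias the estimate or raise the type I error. The planning rates are themselves a judgement made from a pilot of six participants, and that uncertainty may well outweigh a few points of power. It limits the importance of the error but does not make the stated figure right.

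**Conclusion.** The point holds. Under the plan's own rates, 36 completers require 65 enrolled, and 55 give 30.8. Power for the main phase is 81–84% by the methods that reproduce 36, a loss of about 6 to 9 points; the uncorrected chi-square gives 87–88%, still below 90%. By the plan's formula at 31 completers, the risk of missing the planned effect is about 16% instead of 10%.

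This rests on screen failure of 30% of those enrolled, withdrawal of 20% of those allocated, 70% and 25% as rates among completers, and pilot participants staying outside the primary analysis. The shortfall disappears if screen failure is about 18% or less, or if the pilot participants are included.

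**What to change.** In the sample size paragraphs of Section 9, replace the inflation step with 36/(0.70 × 0.80) = 64.3, i.e. 65, and use one enrolment number in both. Then take one of two routes.

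1. **Keep 55 in the main phase and restate its power** as about 84% at two-sided alpha 0.01 (81–84% across the methods that reproduce 36). This corrects the claim but does not restore 90%.
2. **State that the 10 pilot participants, randomised under the same procedures, enter the primary analysis.** Then 65 × 0.56 = 36.4 completers and 90% is met within the approved total. This must be written down before any device-specific pilot data are reviewed. Section 10 has the study team reviewing primary outcome measures at weekly meetings, and the documents do not show whether that condition can still be met. If it cannot, use the first route.

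Either way, Section 9 should say whether pilot participants are in the primary analysis. The cost is the wording of two paragraphs and, under the first route, a slightly less favourable power figure. Neither route adds participants. Reaching 90% without the pilot would mean 65 in the main phase, 10 more than planned.

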 - Any other physical or mental disabilities, or general health problems that could impair the ability to be independently mobile (i.e., walk), participate in the VR walking simulator test or use the prism glasses

Recruitment sources and procedures:

The clinical trial will be conducted in two phases: a pilot phase during which participants will be recruited at Schepens Eye Research Institute and Massachusetts Eye and Ear, followed by the main phase when participants will be recruited at Mass Eye and Ear and other sites outside the MGB network. In this version of the protocol, recruitment sources and procedures are described in detail for the pilot phase at Schepens Eye Research Institute and Massachusetts Eye and Ear. Similar procedures will be used at other sites when they are added to the parent protocol.

- **Who is responsible (role on research team) for identifying and recruiting individuals**
Please see paragraphs below for details of who is responsible for identifying and recruiting participants for each of the recruitment sources.
- **When individuals are recruited**
Participants may be recruited at any time point providing it is at least 6 months since the onset of the HH.
- **Where individuals are recruited**
In the pilot phase of the clinical trial, subjects will be recruited at Schepens and Mass Eye and Ear from the following sources:

1) Vision rehabilitation clinic at MEE

Clinic staff will identify patients that meet our recruitment criteria. Clinic staff will present details about the study to potential subjects when they attend the clinic. Clinic staff will use the information sheet in our recruitment pack (described below). The potential subject can then either contact us

directly (using the contact information on the information sheet) or can complete the permission-to-be-contacted form (part of the recruitment pack described below) and give the form to a clinic staff member. Completed permission-to-be-contacted forms will be returned by clinic staff to the study coordinator. A study team member (study coordinator or research assistant) will then contact the patient by telephone about the study (Telephone script).

2) *Other ophthalmology and rehabilitation clinics in the MGB network*

This will primarily involve recruitment from rehabilitation clinics at Spaulding. Procedures for recruitment will be the same as described in (1) above.

3) *The vision rehabilitation clinic of [name] at Tufts*

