- The subject no longer meets the inclusion criteria (e.g., becomes unable to walk during the course of the study);
- The subject experiences a serious adverse event;
- The subject reports any risky behavior while wearing the glasses such as driving or operating heavy machinery.

Local site restrictions or site-specific procedures:

All sites will use the same procedures.

Description of what happens to participants when the study ends or if a participant's participation in the study ends prematurely.

At the end of the study, subjects will return to the routine care of their own eye doctor. If a subject's participation ends prematurely, they will return to the routine care of their own eye doctor.

Remuneration

Subjects will not be reimbursed for time participating in study visits but will be reimbursed up to \$50 per visit for transportation to Schepens Eye Research Institute/Mass. Eye and Ear.

However, they will be permitted to keep one pair of prism glasses (that cost about \$1000) at the end of the extended wear phase, if considered clinically appropriate. (Subjects who do not complete both periods of the crossover will be requested to return the prism glasses to the site.)

Plans for receiving data from research collaborators outside Mass General Brigham

In the first phase of the clinical trial (pilot data collection at Schepens and Mass Eye and Ear), data will not be received from collaborators outside of Mass General Brigham. Once the multi-site sIRB protocol is implemented, data will be received from research collaborators outside MGB and will be transferred via a secure method (e.g., MGB Dropbox Business). All of the experimental data will be de-identified and will be labeled using only the subject's study ID code. Only consent forms will have identifiable information. Consent forms will be electronically scanned, attested by the site personnel to be a true copy and sent to Schepens by the secure transfer method.

Masking

- Only the person conducting the statistical analyses will be masked to treatment allocation.
- Study participants will not be masked as it would be impossible to do so. (Information about FPPs is readily available on the internet so they could easily determine which pair of prism glasses was already commercially available).

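### Section 9 does not say whether the 10 pilot participants enter the primary McNemar test, and the stated 36 participants and 90% power are reached only if they do

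*Combined protocol and SAP*

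**What the plan says.** Three places bear on the pilot's status.

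- Section 4 (Recruitment sources and procedures): "The clinical trial will be conducted in two phases: a pilot phase during which participants will be recruited" at the two lead institutions, followed by a main phase that adds outside sites.
- Section 6 (data from collaborators outside Mass General Brigham): "In the first phase of the clinical trial (pilot data collection at Schepens and Mass Eye and Ear"), again making the pilot a phase of the trial.
- Section 9 (Sample size estimate): "prior to the main clinical trial, we plan to conduct a pilot of the clinical trial". Its purpose is to verify "study procedures and generate data to verify the sample size calculation". Its 10 enrollees are added to the 55, for a total enrollment of 65.

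The Data analysis plan in section 9 says that improvement rates will be "analyzed using a McNemar test for data combined across both periods of the crossover". It adds "An intention to treat analysis will be used" and codes anyone who withdraws between allocation and the end of the crossover as not improved with either device. It does not mention the pilot. The sizing rests on this sentence: "We therefore estimate that 70% of participants will improve with MPPs and 25% will improve with FPPs". It assumes a 20% overlap and "power of 90% and significance (alpha) level of 1%, 2-tailed test", and arrives at 36 participants, then 54 after losses in one paragraph and at least 55 in the next.

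**The concern.** A confirmatory test needs a fixed population, and here two are available. If the pilot is a phase of the trial, intention to treat would bring its allocated participants into the primary test. If it precedes the main trial and exists to check procedures and sample size, they stay out. The total of 65 does not settle this, because it counts enrollment and does not define an analysis set.

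What is at stake is mainly the power statement. A reader of section 9 would take the 55 to deliver 36 evaluable participants and 90% power without help from the pilot. If that is not so, the trial relies on a figure that only the other reading supports.

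**Working it through.** **Inputs, all from section 9.** Improvement 70% with MPP and 25% with FPP; 20% improve with both; two-sided alpha 0.01; power 90%; 30% screening failure; 20% withdrawal after allocation; 55 main and 10 pilot enrollees.

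**Discordant cells.** MPP only: 0.70 - 0.20 = 0.50. FPP only: 0.25 - 0.20 = 0.05. Sum 0.55, difference d = 0.45.

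**Reproducing the plan's 36.**
n = [z(0.995) x sqrt(0.55) + z(0.90) x sqrt(0.55 - 0.45²)]² / 0.45²
= [2.576 x 0.7416 + 1.282 x 0.5895]² / 0.2025 = 35.09, rounded up to 36. The stated figure is reproduced.

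**Reproducing the plan's 54.** 36 x (1 + 0.30 + 0.20) = 54. The two rates have been added. Since withdrawal applies only to those who pass screening, they act in sequence, and the enrollment needed is 36 / (0.7 x 0.8) = 64.3, so 65.

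**Completers under each reading.**
- Pilot out: 55 x 0.7 x 0.8 = 30.8, about 31 (54 enrolled gives 30.2, about 30).
- Pilot in: 65 x 0.7 x 0.8 = 36.4, about 36.
- Pilot alone: 10 x 0.7 x 0.8 = 5.6, about 6.

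Counting completers is appropriate for power. Withdrawals are coded no/no, which is a concordant pair and adds nothing to the McNemar statistic.

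**Power.** The formula column solves the expression above for power: Phi[(0.45 x sqrt(n) - 1.910) / 0.5895], where 1.910 = 2.576 x 0.7416. The other two columns enumerate all outcomes of the test.

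| Pairs | Formula | Uncorrected McNemar | Exact McNemar |
|---|---|---|---|
| 30 | 82.7% | 86.7% | 81.2% |
| 31 (pilot out) | 84.4% | 88.2% | 83.2% |
| 36 (pilot in) | 91.0% | 93.6% | 90.5% |

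All three methods put the main phase alone below 90% and all 65 enrollees above it. Keeping the withdrawals in as no/no pairs gives much the same answer. The main phase then has 55 x 0.7 = 38.5 allocated, with cells 0.8 x 0.50 = 0.40 and 0.8 x 0.05 = 0.04. For 38 or 39 pairs, power is 81% or 83% (exact) and 87% or 88% (uncorrected).

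**The case against.** **The texts can be reconciled.** The main clinical trial of section 9 may simply be the main phase of section 4, and the passages in sections 4 and 6 concern recruitment and data transfer, not analysis. This stands: the documents do not flatly contradict each other. Section 9 also leans towards exclusion, since it adds the 10 to the 55 and gives them a verification role. A lean is not a rule, however, and the intention-to-treat sentence has no exception for the pilot.

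**The shortfall has another cause.** If the main phase really delivered 36 completers, power would be 90.5% to 94% without the pilot. This also stands. The additive allowance creates the gap, and the pilot's status decides whether it is hidden.

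**Stronger inferences a reader might draw.**

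- *That the population will be chosen after the pilot results are seen.* Section 10 has the team reviewing primary outcomes weekly and about quarterly, and section 6 masks only the analyst. But no passage says the choice will be made then; that would be read into a silence.
- *That the type I error is inflated.* Assuming a null with 27.5% in each discordant cell, 31 main and 6 pilot pairs, and a free choice of the better set, rejection is 1.2% with the uncorrected test and 0.7% with the exact test, against 1%. The plan does not say which version it will use. The effect is negligible.
- *That the two sets often give opposite decisions.* At the design rates they do in 7.4% of trials (uncorrected test, 31 main and 6 pilot pairs). Of these, 6.75 points are significant only when pooled and 0.6 only in the main phase. This mostly restates the power gap.

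**Conclusion.** The point holds as an omission with a consequence for power. The primary analysis set is undefined with respect to the pilot. On the reading that section 9 favours, power is about 83% to 88%, not 90%; the stated 36 and 90% need all 65 enrollees.

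This rests on the plan's improvement rates and overlap, on both loss rates occurring as stated, and on those improvement rates describing completers. The plan's own 20% attrition allowance implies the last of these. If the rates were instead meant to hold for everyone allocated, withdrawals included, 38 main-phase pairs would give 92.6% (exact) to 95.0% (uncorrected), but the attrition allowance would then have no purpose. The 30% is given as an upper figure, so milder screening losses would narrow the gap.

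The documents do not support a finding of meaningful type I inflation or of a planned after-the-fact choice of population. The point should be settled in the text, but it does not undermine the design.

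**What to change.** In section 9, name the primary analysis set before any further review of outcomes by device. Main-phase participants only is the choice consistent with the sample size text, and it keeps data used to check the effect assumption out of the test that confirms it. Report a McNemar test on pilot and main phase pooled as a labelled sensitivity analysis. Declaring the pilot included would also remove the ambiguity, but it sits less well with the pilot's stated purpose.

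Replace the 90% with the power the chosen set delivers: about 83% to 88% for the main phase alone, naming the version of the test. If 90% is to be kept with the pilot excluded, about 65 main-phase enrollees are needed, 75 in total with the pilot.

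Rewording sections 4 and 6 is optional once section 9 names the set. Without re-sizing, the cost is a few sentences, a less favourable stated power, and about 6 pilot completers outside the primary test. Re-sizing would add 10 enrollees.
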